#### 6. Analyses of the Relationship between Application Status (before Compensation examination vs. after, before receiving claim judgment vs. after) and Treatment Attendance (Evaluative Specific Aim3: Long-term attendance at treatment will be significantly impacted by the occurrence of the Compensation examination and determination of award):

Attendance at treatment will be regressed on time-varying covariates reflecting having had a Compensation examination, and having had a Compensation claim approved by the Veterans Benefits Administration. A secondary analysis will consider whether these time-varying covariates will significantly interact with attitudes concerning how disability is awarded.

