#### 3. Schedule of Assessments:

Visit	Domain	Assessment
BL	Characterize Participants	Baseline Questionnaire (including TBI screen) MOCA
BL	Beliefs about Compensation	Disability Application Appraisal Inventory Disability Beliefs Scale
BL	Substance Use	SCID substance abuse module
BL, 4, 12	Substance Use	Substance Use Calendar
BL, 12	Alcohol Use	Ethyl Glucoronide
BL	PTSD	Life Events Checklist and Military Sexual Trauma Screen
4	Process	Veterans' understanding of the study assessments and their relationship or lack thereof to the C&P exam
BL, 4, 12	PTSD	CAPS
BL, 4, 12	Other Psych	Beck Depression Inventory II
BL, 4, 12	Service Use	Service Use Calendar
BL, 4, 12	Process	Stage of Change
BL, 4, 12	Other Psych	Response to Stressful Experiences Scale
At Rx	Process	Satisfaction with Therapy
End-of-Study	Chart Review and Database Extraction	Review of Service Use and Diagnoses from VA Databases; Reports from Compensation Examinations; Disability Determination by VBA; Distance between Veterans' addresses and VA site

Justification for Schedule of Assessments: The initial 4-week assessment follow-up date was chosen because results of Motivational Interviewing interventions have been detectable this quickly in other studies (Burke, Arkowitz et al. 2003); the later, week 12 assessment will allow for detection of later-emerging effects of other VA treatments preferentially attended by Veterans who received the SBIRT intervention.

The end-of-study service use assessments will be conducted in the middle of year 4. Virtually all of the last cohort of study participants will have service use data for the three months after claims adjudication available at that time; the highly-publicized delays in the awarding of benefits generally are caused by delays prior to the Compensation evaluation.

Time to Complete Assessments: The baseline assessment will take approximately two and a quarter hours to complete. Approximately 45-60 minutes are allotted for the CAPS and Life Events Checklist; ten minutes for each of the baseline questionnaires, SCID substance abuse module, and service use calendar; and twenty minutes for each of the other baseline assessments.

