#### H. Chart Review and Database Extraction

1. Therapy Attendance and Service Use Outcomes. Episodes reflecting use of VA substance abuse, specialized PTSD and other mental health treatment will be collected from VA administrative records as described previously (Harpaz-Rotem, Rosenheck et al. 2009). The investigators have extensive experience analyzing VA service use data. [name] is a national authority on service use analyses.

The Austin Information Technology Center provides the service use data for [name] analyses. The Austin databases hold data from all Veterans who received any services from anywhere in VA. The Patient Treatment File contains all episodes of inpatient care delivered within the VA system. The Outpatient Encounter File documents all outpatient VA service use. VA bed section codes indicate hospitalization on specialized units and VA clinic codes indicate outpatient treatment in specialized clinics. In a recent manuscript, [name] describes analysis of psychotherapy service use codes from these databases (Hunt and Rosenheck, 2011), which will be extracted as psychotherapy participation may reflect a more specific measure of engagement in treatment than broader measures.

Service use data will be collected from three months before the Compensation claim was filed until three months after claims adjudication. We will also collect the date Veteran was separated from military service to determine when VA services became available to each Veteran.

2. Compensation examinations of each Veteran will be reviewed by research assistants who will complete a chart extraction form. The extraction form collates the following information:

- i. Clinician diagnosis from C&P exam
- ii. Alcohol Use

-- Level of detail describing alcohol use (No mention, Impression but no number of drinks, or number of drinks---including a statement that there has been no recent use).

- Amount of alcohol reported used in drinks/drinking day
- Alcohol Use Consequence (no mention, consequences listed)
- Alcohol Use Disorder Diagnosed (no diagnosis; use noted but no judgment that it is a problem, or merits intervention; rule-out alcohol use diagnosis made; alcohol use diagnosis made)

iii. Other Substance Use (characterized as for alcohol, with delineation of particular drugs)

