3. Award determination by VBA: Award determination will also be the dependent measure in proposed secondary analyses. The data collected will be whether any benefit was awarded, and the percentage service connection awarded.

4. The VA databases will be used to identify all non-exclusive psychiatric diagnoses, as defined in the DSM-IV and DSM-V, ICD 9 and ICD 10.

5. Distance from VA: Veterans' addresses collected upon enrollment will be converted into distance from the nearest VA facility using Global Information System (G.I.S.) mapping (Fortney 2000). Participants and VA treatment facilities will be geocoded by street level (the G.I.S. will use the street address) to calculate driving distance as a measure of treatment accessibility. Distance from treatment has been associated with receipt of fewer services (Rost, Fortney et al. 2002).

6. Chart review to determine presence of a substance abuse disorder at time of Compensation.

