#### J. Data Analysis for Evaluative Component:

1. Sample Analyzed for Evaluative Component: The effects of substance abuse on outcomes will be analyzed in the sample of 560 participants who did not receive SBIRT, 80 of whom report risky alcohol/substance use and 480 who did not.

2. Data Reduction: Substance use disorder, PTSD diagnosis, and treatment attendance measures are being collected from more than one source. It is important to reduce the data prior to subsequent analyses to identify the outcomes that will be used in the analyses. These data reduction approaches are shown below:

a. The presence or absence of an Alcohol Use disorder at the time of the Compensation examination will be determined by the best estimate procedure developed by Spitzer and colleagues for validating DSM diagnoses (Spitzer, 1983). This procedure involves reviewing all available sources of information, which for this measure will include the SCID interview, Compensation examination report, substance use calendar, chart review and ICD-9 diagnoses.

A sensitive definition of alcohol use disorder will be employed, and the Principal Investigator will review all cases for which the Compensation Examination and SCID diagnosis are discordant. The reasons to use a sensitive but possibly less specific definition of alcohol use disorder are that an extensive literature documents that there are few "false positive" reports of alcohol and other substance abuse (Kosten and Rounsaville 1992). In a population of Veterans applying for PTSD-based disability, Veterans drinking substantial amounts of alcohol are likely to meet criteria for either Abuse or Dependence, and people with PTSD are particularly vulnerable to the psychological disruptions caused by drugs of abuse (Back, Brady et al. 2006). The same approach will be taken to arriving at best estimate diagnoses for other substances of abuse. The stability of the results will be determined by substituting alternate definitions of the substance use construct.

Descriptive analyses will be conducted to describe the agreement between the different sources of information. For example, the definition of alcohol-use disorders will be compared between the SCID Diagnoses during the assessment battery and the Compensation examinations. Preliminary descriptive and ROC analyses will be conducted of the accuracy of the Compensation examinations for determining alcohol use disorders with the validating criterion being the best estimate diagnosis.

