b. Treatment attendance will be determined from Austin databases and from the self-reported Service Use calendar. Self-report data will be used for outcomes that cannot be determined from the Austin databases---use of non-VA services, and whether substance abuse was addressed during a counseling session.

Because *sustained* attendance has been more strongly associated with benefit from substance abuse treatment than intensity of treatment (Ritsher, McKellar et al. 2002; Moos and Moos 2003), attendance at treatment will be determined as a dichotomous variable on a week-by-week basis. The extent of therapy attendance will be determined separately for three types of treatment: Mental Health in PTSD specialty clinics, Mental Health in non-specialty clinics, and Substance Abuse specialty treatment.

Each category of therapy contacts will be subdivided as treatment with and without psychotherapy, creating six total therapy attendance measures. Analyzing the subset of contacts representing psychotherapy visits will cull for visits that represent willingness to discuss the problem behavior/symptoms. [name] has utilized methods identifying psychotherapy stop codes in the Austin databases in a completed service use analysis (Hunt and Rosenheck, 2011).

c. Exploratory analyses will be conducted concerning the agreement of Compensation examination PTSD diagnoses and CAPS-generated PTSD diagnoses. ROC analyses will be conducted on the accuracy of the Compensation examination diagnoses of PTSD with the

validating criterion being a diagnosis derived from the CAPS interview. The CAPS interview, like the Compensation examination, measures the specific DSM IV criteria for PTSD, so concordance is expected to be high. A diagnosis of PTSD will be derived from the CAPS using the “1/2” rule, in which (1) a core PTSD symptom is counted as present when its frequency is rated as a ‘1’ or greater and its intensity is rated as a ‘2’ or greater; and (2) total CAPS severity  $\geq 45$  (Schnurr, Friedman et al. 2005). This strategy ensures that the DSM-IV symptom criteria are met and that severity is sufficiently high. Exploratory analyses will examine characteristics associated with discordance between Compensation examination and CAPS interview diagnoses (diagnosis on CAPS but not on Compensation examination and vice versa).

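### The Aim 3 model (J.6) has a term for claim approved but none for claim decided, so it cannot give the before-versus-after-judgment contrast in its own heading

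*Combined protocol and SAP*

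**What the plan says.** Section J.6 (Evaluative Specific Aim 3) defines application status in its heading by two contrasts: before versus after the examination, and "before receiving claim judgment vs. after". The analysis is then given in one sentence: "Attendance at treatment will be regressed on time-varying covariates reflecting having had a Compensation examination, and having had a Compensation claim approved". In a further step, the same two covariates are interacted with attitudes about how disability is awarded.

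The data behind this analysis are described elsewhere:

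- **Follow-up window (H.1):** "Service use data will be collected from three months before the Compensation claim was filed until three months after claims adjudication". The justification under the Schedule of Assessments likewise expects "service use data for the three months after claims adjudication" for virtually all of the last cohort. Neither place limits the window to approved claims.
- **Award data (H.3):** "The data collected will be whether any benefit was awarded, and the percentage service connection awarded". Denial can therefore be identified. The date of the decision is not listed.
- **Outcome (J.2.b):** "attendance at treatment will be determined as a dichotomous variable on a week-by-week basis".
- **Sample (J.1):** the "sample of 560 participants who did not receive SBIRT".

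No section adds a term for a denied claim or for a decision of either kind.

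**The concern.** The heading asks what happens to attendance once the claim has been judged. The model tells the analyst only when a claim was approved. For a denied Veteran the approval term never switches on, so the three months after denial are treated as if the claim were still open.

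Two things follow. The contrast in the heading is not a function of the model's coefficients. And the coefficients that are estimated change meaning: approval is compared with a mixture of waiting and post-denial weeks, and the examination effect averages over the same mixture. If denied Veterans leave treatment, approval can appear to raise attendance when it does nothing. The attitude-moderation part of Hypothesis 3 inherits the problem because it reuses the same terms.

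**Working it through.** The plan states no sample size, power or effect size for Aim 3, so there is no planned figure to reproduce. The check has three parts.

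**1. Coding.** Values of (examination held, claim approved) by week:

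| State of the claim | Code |
|---|---|
| Before examination | (0, 0) |
| Examined, decision pending | (1, 0) |
| After denial | (1, 0) |
| After approval | (1, 1) |

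Pending and post-denial rows are identical, so no estimator using these two terms can separate them. This holds for any effect size and any timing.

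**2. How many Veterans.** Award rates are from the Background section on Compensation examinations. Share affected = 1 − award rate; count = 560 × share, if all 560 receive a decision.

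| Award rate | What it describes | Share affected | Count of 560 |
|---|---|---|---|
| 55.6% | recent PTSD claims | 0.444 | 249 |
| 33% to 72% | PTSD, older study | 0.67 to 0.28 | 375 to 157 |
| 80% | PTSD after appeals, not an initial rate | 0.20 | 112 |
| 88% | OEF/OIF, any disability, as of 2005 | 0.12 | 67 |

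**3. Size of the distortion (illustration).** The documents give no denial effect and no examination-to-judgment gap. Assumed: denial changes attendance by −10 percentage points, approval by 0, examination by 0; 55.6% awarded; 13 weeks of follow-up after judgment (the three months in H.1).

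The simplest case is a pooled linear fit without a time trend. The false examination effect is then the mean of the (1, 0) weeks, and the false approval effect is its negative. With gap g in weeks, the post-denial share of the (1, 0) weeks is

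0.444 × 13 / (g + 0.444 × 13) = 5.772 / (g + 5.772).

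- g = 4: 5.772 / 9.772 = 59%, false approval effect +5.9 points
- g = 13: 5.772 / 18.772 = 31%, +3.1 points
- g = 26: 5.772 / 31.772 = 18%, +1.8 points

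A within-person (demeaned) linear model gives the following noise-free coefficients. The ranges cover two assumed spreads of pre-examination time, 13–39 and 26–65 weeks:

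| Gap | Approval, no trend | Approval, linear trend added |
|---|---|---|
| 4 weeks | +4.6 to +5.1 | +5.0 to +5.2 |
| 13 weeks | +1.8 to +2.2 | +2.6 to +3.4 |
| 26 weeks | +0.8 to +1.1 | +2.2 to +3.6 |

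The true approval effect in every cell is 0. At 13 weeks the false examination effect is −2.7 to −2.8 without a trend. With a trend its sign depends on the window (+0.9 to −1.4). J.6 states no trend. The Schedule of Assessments says that "delays in the awarding of benefits generally are caused by delays prior to the Compensation evaluation", which points towards the shorter gaps.

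At 13 weeks with 26–65 pre-examination weeks and no trend, the false approval effect is +3.0 at a 33% award rate, +1.5 at 72%, +1.1 at 80% and +0.7 at 88%. All these figures scale with the assumed denial effect: zero if it is zero, opposite in sign if denial raises attendance.

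**The case against.** Four points can be made for the plan.

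- **The wording is loose.** The sentence speaks of covariates reflecting these events and gives no equation, so an analyst who reads the heading too could build a decided term. That is possible, but nothing instructs it, and the choice would then be made after the data are in hand.
- **An award-only question is coherent.** Hypothesis 3 speaks of determination of award, and the Background cites the claim that Veterans leave treatment once an award is made. Some denied claimants may also be appealing. This narrower reading is legitimate, but the heading's claim judgment does not depend on outcome, so heading and sentence still disagree. Under the narrow reading the reference group still mixes pending and post-denial weeks.
- **The contrast is diluted rather than lost if judgment affects everyone alike.** With a true effect of −10 points after both approval and denial, the planned approval coefficient is −7.8 without a trend and −7.4 with one (13-week gap, 26–65 pre-examination weeks). This stands for that special case, but the specified model cannot show whether it applies.
- **The sizes rest on assumptions.** This stands. They vary with award rate, gap, trend and estimator, and J.6 does not name the estimator. The coding problem does not depend on any of them.

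It is also true that this is the third hypothesis of an observational component and that no data would be lost.

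**Conclusion.** The concern holds. As written, J.6 does not estimate the before-versus-after-judgment contrast in its heading, because pending and post-denial weeks share one code. That conclusion needs no numerical assumption.

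The documents support about 249 of 560 Veterans affected at the 55.6% PTSD award rate. Across all the award rates cited the count runs from 67 to 375. Under the assumed 10-point denial effect, the false approval effect at a 13-week gap is about 2 to 3 points across the models tried, and about 5 to 6 points at 4 weeks. If denial does not change attendance there is no bias, but the plan gives no grounds for assuming that and no means of testing it. The model should be corrected before analysis. The randomized SBIRT comparison is not affected.

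**What to change.** In J.6, replace the approval covariate with two time-varying terms: judgment received, and judgment received × approved. Coding approved and denied as separate states, each against pending, is equivalent. Test the two terms jointly for the determination part of Hypothesis 3, and carry both into the attitude interactions. In H.3 and the Schedule of Assessments, name the adjudication date as an extracted item that starts these terms.

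If only awards are of interest, reword the heading to say so and still separate denied from pending weeks. Optionally, state how a denial reversed on appeal within the three-month window is coded.

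The cost is one extra model term and two sentences. Award status is already collected, and the H.1 window cannot be built without the adjudication date. The approval coefficient becomes slightly less precise: in the within-person illustration with independent weekly errors, its standard error rises by 2–8% at a 13-week gap, 15–19% at 4 weeks and 0–8% at 26 weeks.

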#### 7. Exploratory Analyses of Predictors of Compensation Award: Secondary analyses will be conducted to determine factors associated with receipt of award. Anticipated factors associated with receipt of award include site, demographic factors, depression and CAPS severity. A supplementary analysis will determine whether Veterans' likelihood of obtaining Compensation is impacted by behaviors around the time of the examination. The independent contribution of

each of the following to receiving Compensation will be considered in a regression analysis, after covarying for demographic and other factors: i) not having substance use noted in the medical chart before the Compensation examination, ii) attendance at VA mental health treatment before the Examination, iii) attendance at non-VA mental health treatment before examination, iv) having been prescribed psychotropic medication.

8. Other Exploratory Analyses: The covariates in the analyses of outcomes are of interest and will be considered in more in-depth secondary analyses. If suggested in bivariate analyses, the independent contribution of such factors as gender, age, depression, legal status, social support, employment and cognitive function will be described in separate analyses.

We will describe the rates of HIV risk behaviors among the study population, both with and without substance use. Knowing these rates will give policymakers some information about the extent of the problem of HIV-risk behavior, and the usefulness of focusing interventions on these Veterans. We will also determine the independent contribution of substance use, PTSD severity, and attendance in treatment on engaging in HIV-risk behaviors over time, using random effects regression, as outlined in #4 above.

As psychiatric symptoms and substance use predict higher rates of sexual risk behavior, we will also explore whether changes in those variables are associated with change in sexual risk behavior.

#### 2. Evaluation of Treatment Effects:

Evaluation of comparability of baseline characteristics of the two client groups will be conducted using chi-square tests for categorical variables and t-tests for continuous variables. If an unexpected difference is found and is related to the outcome, the potentially significant confounding variable will be added to the primary outcome analysis as a covariate.

The principal strategy for assessing the efficacy of the study treatments will be random effects regression, as described for the analysis of the effects of substance use on other outcomes. The focus of these analyses will be the ‘treatment group by time effects’ for each

hypothesis, and whether the slopes, or rates of change, of Veterans assigned to SBIRT differ from the slopes of those assigned to No-Additional-Treatment. The model will include appropriate covariates and the contrasts of SBIRT versus Control. The effects of site and the site-by-treatment interaction will be determined.

Our principal data analyses will be conducted on the intention-to-treat sample. We will attempt to follow all participants for assessments regardless of their retention in treatment. Intention-to-treat analyses will be supplemented by analyses to describe the consistency of findings across different definitions of the sample: e.g., treatment-exposed and treatment completers.

Secondary analyses will be conducted to account for the possibility that days without substance use data (scored as missing) are not randomly distributed. In these analyses, variables that distinguish people with missing substance use data from those with complete data will be included in the analyses as covariates or auxiliary variables (Graham, 2003).

A linear effect of time on outcome variables is being hypothesized but ancillary analyses will be conducted to determine if the effect of SBIRT treatment is better explained by a quadratic function, given the possibility of deceleration in rate of change.

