**E. Description of SBIRT/Therapy Procedures: A manual describing SBIRT-VA is attached as Appendix 1.**

1. Logistics

a. Setting: The therapist will contact participants to schedule the therapy. If the Veteran does not want to come for face-to-face counseling, the therapist will offer to conduct the counseling by telephone. The counseling by telephone will have the same content as the face-

to-face counseling, except that Veterans will be asked to verbally indicate the values that are most important to them instead of sorting physical cards with this information. Although less compelling than the data for face-to-face counseling, SBIRT has been conducted effectively by phone and allowing for counseling by phone is feasible and allows for Veterans who otherwise would not get study counseling to get it.

- b. A videotape will be set up to rate the study therapist (described later)
- c. Frequency: Therapy will be conducted in a single 60-minute session.

2. Therapist Stance: There are several acronyms (OARS, FRAMES) to describe the methods Motivational Interviewers are asked to follow. Key features of Motivational Interviewing are

a. Expressing Empathy: The therapist will elicit and empathize with the emotions that accompany the Veteran's disability application. Veterans experience considerable distress during Compensation examinations (Sayer, Spoont et al. 2005).

b. Supporting Self Efficacy: The therapist will reinforce any belief the Veteran has that change is possible, that reduced substance use is achievable, or that substance abuse treatment works. For example, the therapist can point out the initiative the Veteran has taken in facing his or her disability

c. Rolling with Resistance: The therapist does not argue with the Veteran's resistance, but "rolls with it." The therapist will use the Veteran's "momentum" to further explore the Veteran's views. By allowing the Veteran full-throated expressions of resistance to change ("I like to drink and nobody can tell me not to"), the therapist may amplify and subtly undermine the Veteran's statement "You feel you like to drink so you will, no matter what anyone says." A response by the Veteran reflecting change talk would be "Well, I don't drink at work," which would be followed up by inquiries about work-related concerns.

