#### E. No-Additional-Treatment Control Condition:

As noted in the Single Patient Flow Chart, veterans assigned to the control condition will not receive any study-related therapy. A Veteran who completes a Compensation examination ordinarily has no further treatment, referral or debriefing as part of the Compensation examination.

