#### I. Measures Collected from Therapists after SBIRT Counseling Sessions

1. Overview: It is important to measure the fidelity and skill with which SBIRT is delivered, and to measure non-specific but potentially important ingredients such as general supportiveness of the therapist. Each therapists' first eight Veterans treated with SBIRT will be videotaped except if the Veteran asks not be videotaped. Subsequently, a random sample of 10% of sessions will be videotaped and rated. Therapists will set up the recording equipment and sound-amplifying microphone. The camera will be trained on the therapist.

2. Rating of Therapy Videotapes: Videotapes will be rated using ratings drawn from the Yale Adherence and Competence Scale (Carroll et al., 2000) and the current Benefits Counseling study. Standard procedures will be used to rate the videotaped sessions. Two raters blind to the study design will be trained by the P.I. and will rate sessions. During rater training, raters will review the rating form, anchor points, and procedures to rate the sessions. They will then view a videotape, rate it, and review the ratings with the P.I. Discrepancies between the raters will be reviewed and the process will be repeated for successive tapes until adequate inter-rater reliability is achieved. After the two raters have been trained, they will together rate 20% of the collected videotapes.

3. Videotape Rating Scale: Raters will indicate the frequency and extensiveness with which an element of the therapy is covered during a session using a Likert scale anchored by 1- not at all and 7- extensively, with descriptions of what constitutes meeting these anchors. A second scale rates therapist skill level at covering the element (if covered) on a scale anchored by 1- very poor to 7- excellent. The dimensions of adherence and competence are only modestly correlated and thus reflect different aspects of treatment (Carroll, Nich et al. 2000). The subscales and items will determine:

- i. if essential elements of SBIRT were delivered (assessment, feedback, referral)
- ii. use of Motivational Interviewing (empathy, developing discrepancy, rolling with resistance)
- iii. general factors (optimism, discussion about VA, general inquiries)
- iv. proscribed elements (convey value judgments concerning disability, substance use)

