4. Time Spent Providing Counseling: A contact log will be completed for each phone or face-to-face encounter, including scheduling. The contact log will document whether there was a scheduled contact that was not attended, the date and time of contact, type of contact (face-to-face, phone, cancelled appointment), and time spent in minutes.

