### 5. Evaluation of Process Measures

Group X Time random effects regression analyses will be conducted to determine differential effects of time on Stage-of-Change, which is collected at multiple time points. The Likert-scaled therapy process ratings and other measures reflecting single values (e.g. duration of therapy sessions) will be compared between groups using ANOVAs.

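### The treatment-exposed and completer samples are not defined for a control arm that gets no study therapy, and the between-group ANOVAs of therapy ratings and session duration have data in the SBIRT arm only

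*Combined protocol and SAP*

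**What the plan says.** - **Arms.** The section on the No-Additional-Treatment control condition states that "veterans assigned to the control condition will not receive any study-related therapy". For the SBIRT arm, the Logistics paragraph of the therapy description states: "Therapy will be conducted in a single 60-minute session".
- **Analysis sets (K.2, Evaluation of Treatment Effects).** "Our principal data analyses will be conducted on the intention-to-treat sample", and follow-up is attempted whether or not a Veteran stays in treatment. Supplementary analyses are then to describe "consistency of findings across different definitions of the sample: e.g., treatment-exposed and treatment completers". Neither sample is defined, and nothing is said about which controls belong to them.
- **Process measures (K.5).** After a Group X Time analysis of Stage-of-Change, the plan adds: "The Likert-scaled therapy process ratings and other measures reflecting single values (e.g. duration of therapy sessions) will be compared between groups using ANOVAs".
- **Source of those measures (section I).** The section covers measures taken after SBIRT sessions. On ratings: "Each therapists' first eight Veterans treated with SBIRT will be videotaped", followed by a random 10% of later sessions. Duration comes from a contact log that records "type of contact (face-to-face, phone, cancelled appointment), and time spent in minutes". The assessment schedule places therapy satisfaction at the treatment visit.

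**The concern.** Both K.2 and K.5 read as though each arm had a therapy to attend. K.4 (response to counselling of any kind) and the safety monitoring plan (two therapies) are worded in the same way. Only one arm has a therapy.

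In K.2, receipt or completion of therapy can separate Veterans only within the SBIRT arm. If SBIRT no-shows are removed and all controls stay, the comparison is no longer between randomized groups. Veterans who keep a counselling appointment may also be those who attend other care, and weeks attending care is the second primary outcome. These analyses are there to show whether the intention-to-treat result is consistent, and agreement produced partly by selection would not show that.

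In K.5, a comparison of session ratings and minutes between SBIRT and control has nothing on the control side.

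**Working it through.** **1. The plan's own figure.** Inputs from the Clinical Trial power paragraph: effect 0.50, power 0.80, alpha 0.05. A two-sided two-sample t test needs 127.5 in total, rounded up to 128 (power 0.801 at 64 per arm). Allowing 20% loss, 128 / 0.80 = 160. Both stated numbers reproduce. The design section puts 80 of the 160 in the control arm, so there are 80 per arm. The sample size is not in question here.

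**2. Which arm supplies data.**

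| Planned analysis | SBIRT | Control |
|---|---|---|
| K.2 treatment-exposed | Veterans who attended the session | none can qualify |
| K.2 treatment completers | nearly the same Veterans, as there is one session | none can qualify |
| K.5 therapy ratings | taped sessions | none |
| K.5 session duration | contact log | none |
| K.5 Stage-of-Change, Group X Time | baseline, weeks 4 and 12 | baseline, weeks 4 and 12 |

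**3. What K.2 can mean.** Read literally, the control sample is empty and there is no comparison. Read in the only workable way, SBIRT falls from 80 to 80a, where a is the share attending, and control stays at 80. That gives about 77 v 80 at a = 0.96, 64 v 80 at 0.80 and 48 v 80 at 0.60. The 0.96 comes from the feasibility section (75 patients in an earlier study of vocational counselling around Compensation examinations). The other two values are assumptions.

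**4. Illustrative size, with no true effect.** Let D be the outcome gap, in SD, between SBIRT Veterans who would and would not attend. The documents give no D, so 0.2 to 0.8 is assumed.

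- Bias b = (1 − a) × D
- SE = √(1/80 + 1/(80a))
- Chance of a false two-sided 0.05 result = Φ(b/SE − 1.96) + Φ(−b/SE − 1.96)

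Example: a = 0.80 and D = 0.8 give b = 0.20 × 0.8 = 0.16, SE = √(0.0125 + 0.015625) = 0.168, and a chance of 0.159.

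| a | b, D = 0.2 to 0.8 | False-positive chance |
|---|---|---|
| 0.96 | 0.008 to 0.032 | 0.050 to 0.055 |
| 0.80 | 0.04 to 0.16 | 0.057 to 0.159 |
| 0.60 | 0.08 to 0.32 | 0.072 to 0.418 |

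A second parameterisation lets attendance follow a latent trait correlated r = 0.3 to 0.5 with the outcome, with b = r × φ(c)/a and c the (1 − a) normal quantile. It gives 0.03 to 0.05, 0.11 to 0.18 and 0.19 to 0.32 SD at the same three attendance rates.

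Both calculations concern a difference in means. K.2 tests a difference in slopes. A trait that raises attendance equally in every week shifts the intercept and leaves the slope alone. It biases the slope only so far as it is related to change over time. The table therefore shows how sensitivity grows as attendance falls. It does not forecast bias in the planned model.

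**5. K.5.** One randomized group has data, so the between-group degrees of freedom are 1 − 1 = 0 and F is undefined. Entering zero minutes for controls would return a number, but it would only restate the assignment.

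**6. The complier alternative.** Controls have no SBIRT session, so in its simplest form the estimate is the intention-to-treat difference divided by a: a factor of 1/0.96 = 1.04, 1/0.80 = 1.25 or 1/0.60 = 1.67. The standard error grows by about the same factor.

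**The case against.** The strongest reply is that K.2 never specifies a one-arm filter. It gives two sample names as examples, and retention of every control is a reader's inference. Intention-to-treat is principal, and the other analyses only describe consistency, so no confirmatory claim rests on them. The only attendance figure in the documents is 96%, and the telephone option and several contact routes also favour high uptake. The direction of any bias is assumed as well: some randomized Veterans are already in treatment, and the documents do not show that no-shows use less care.

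Most of this stands and limits the weight of the point. It does not rescue the text. A sample defined by receipt of therapy still needs a rule for an arm without therapy, and none is given. The 96% comes from a different intervention, so it supports high attendance without establishing it.

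On K.5, groups could mean sites or therapists. The sentence just before uses Group X Time, which points to the randomized arms. If sites were meant, the plan should say so.

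Against the remedy, the complier estimate adds little at 96% uptake. Its exclusion restriction is also open to question, because notification, scheduling and therapist contact can occur without a session. Both objections are fair and should be stated with the result.

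**Conclusion.** The point holds as two faults in non-primary analyses.

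- **K.2:** the exposed and completer samples are undefined for the control arm, nearly coincide for a one-session therapy, and in any workable form filter SBIRT only.
- **K.5:** the ANOVAs of therapy ratings and session duration cannot be run as SBIRT versus control. This rests on reading groups as the randomized arms and needs no numerical assumption.

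Selection bias in K.2 is negligible if attendance is near 96%. It could matter if attendance is much lower, but its size then depends on an assumed attendance rate, an assumed prognostic gap and an assumed link to change over time.

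A reader might infer more, and the documents do not support it:

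- that the efficacy conclusion is compromised: intention-to-treat is principal and untouched;
- that the plan prescribes dropping SBIRT no-shows against all controls: it is silent on controls;
- that the bias is a known share of the planned 0.50 effect: that effect is a difference in linear trends, and the calculation above is a mean shift;
- that all of K.5 fails: Stage-of-Change is collected in both arms and its analysis stands.

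**What to change.** **K.2.** Replace the exposed and completer samples with one supplementary complier average causal effect estimate. Use assignment as the instrument and attendance at the SBIRT session, from the contact log, as the exposure, and keep all randomized Veterans. Say what counts as attendance, including by telephone. State the exclusion restriction and why it may be doubted, and note that the interval will be wider than that of a completer comparison. Estimating it on per-Veteran totals (weeks attending treatment, days of use) would avoid fitting it to repeated binary data. Report the attendance rate beside it.

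**K.5.** Delete the SBIRT-versus-control ANOVAs of therapy ratings and session duration. Describe these measures within SBIRT, by site and by face-to-face or telephone delivery. Keep the Stage-of-Change Group X Time analysis.

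**Cost.** Revised wording and one supplementary model that needs some specification. No new data are needed, and the sample size and the principal analysis do not change. At very high attendance the complier estimate will differ little from intention-to-treat.
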